4.5.3 Converting from or to Apixaban

Switching from VKA to apixaban: VKA should be discontinued and apixaban started when the INR is below 2.0.

Switching from apixaban to VKA: apixaban may affect INR, so that INR measurements during co-administration with VKA may not be useful for determining the appropriate dose of VKA. If continuous anticoagulation is necessary, discontinue apixaban and begin both a parenteral anticoagulant and VKA at the time the next dose of apixaban would have been taken, discontinuing the parenteral anticoagulant when the INR reaches an acceptable range per institutional standards.

Switching between apixaban and anticoagulants other than VKA: discontinue one being taken and begin the other at the next scheduled dose.

4.6 Blinding/Unblinding

Not applicable, this is an open label study.

4.7 Treatment Compliance

Each time study medication is dispensed, compliance will be reinforced.

For inpatients, apixaban will be administered in the clinical facility under the supervision of clinical staff. The date and volume or dosage of administered drug will be recorded at the clinical site by clinical or research personnel in the subject’s diary and eCRF. If an infant or a young child regurgitates a portion of or the entire drug product during or after administration, this should be recorded in the eCRF.

At each study visit, the subject/parents should bring the study medication and compliance will be assessed based upon subject’s/parents interview and a count of the tablets or volume of solution returned. Compliance should be between $\geq 80\%$ and $\leq 120\%$ of that prescribed, excluding any protocol defined dose interruption period. The investigator (or designee) will record the amounts of study medication dispensed and returned at each visit, as well as document reasons for non-compliance in the source document. The dates of all study medication dosing, including interruptions, missed doses or overdose, must be recorded on the CRF. If a subject is not $\geq 80\%$ compliant after exclusion of the protocol defined dose interruption period, then the period of non-compliance should be noted as a protocol deviation and the sponsor should be notified. The subject should be re-educated regarding medication compliance.

4.8 Destruction or Return of Investigational Product

For this study, IP (those supplied by BMS, a vendor, or sourced by the investigator) such as partially used study drug containers may be destroyed on site.

| If... | Then... |
|---|---|
| IP supplied by BMS (including its vendors) | Any unused IP supplied by BMS can only be destroyed after being inspected and reconciled by the responsible Study Monitor unless IP containers must be immediately destroyed as required for safety, or to meet local regulations (e.g., cytotoxics or biologics). If IP will be returned, the return will be arranged by the responsible Study Monitor. |
| IP sourced by site, not supplied by BMS (or its vendors) (examples include IP sourced from the sites stock or commercial supply, or a specialty pharmacy) | It is the investigator’s or designee’s responsibility to dispose of all containers according to the institutional guidelines and procedures. |

It is the investigator’s or designee’s responsibility to arrange for disposal, provided that procedures for proper disposal have been established according to applicable federal, state, local, and institutional guidelines and procedures, and provided that appropriate records of disposal are kept.

The following minimal standards must be met:

- On-site disposal practices must not expose humans to risks from the drug
- On-site disposal practices and procedures are in agreement with applicable laws and regulations, including any special requirements for controlled or hazardous substances
- Written procedures for on-site disposal are available and followed. The procedures must be filed with the site's SOPs and a copy provided to BMS upon request
- Records are maintained that allow for traceability of each container, including the date disposed of, quantity disposed, and identification of the person disposing the containers. The method of disposal, i.e. incinerator, licensed sanitary landfill, or licensed waste disposal vendor must be documented
- Accountability and disposal records are complete, up-to-date, and available for the Monitor to review throughout the clinical trial period

It is the investigator's or designee's responsibility to arrange for disposal of all empty containers.

If conditions for destruction cannot be met the responsible Study Monitor will make arrangements for return of IP provided by BMS (or its vendors). Destruction of non-IP sourced by the site, not supplied by BMS, is solely the responsibility of the investigator or designee.

Please refer to [Section 9.2.2](#) for additional guidance on IP records and documentation.

4.9 Return of Study Drug

If study drug will not be destroyed upon completion or termination of the study, all unused and/or partially used study drug that was supplied by BMS must be returned to BMS. The return of study drug will be arranged by the responsible Study Monitor.

It is the investigator's responsibility to arrange for disposal of all empty containers, provided that procedures for proper disposal have been established according to applicable federal, state, local, and institutional guidelines and procedures, and provided that appropriate records of disposal are kept.

4.10 Retained Samples for Bioavailability / Bioequivalence

Not applicable.

5 STUDY ASSESSMENTS AND PROCEDURES

5.1 Flow Chart/Time and Events Schedule

Table 5.1-1: Screening Procedural Outline (CV185362)

| Procedure | Consent/ Screening Visit Day -21 to 1 | Randomization Visit Day 1 | Notes |
|---------------------------------------|---|---------------------------------|--|
| Eligibility Assessments | | | |
| Informed Consent | X | | Informed consent must be signed prior to initiating any study procedures |
| Inclusion/Exclusion Criteria | X | X | Includes assessment of the indication for thromboprophylaxis |
| Medical History | X | | Includes collection of disease specific medical and surgical history and primary diagnosis |
| Physical Measurements | Height, Body Weight, and calculated Body Mass Index | Body Weight | Body weight must be ≥ 3 kg |
| Concomitant Medication Assessment | X | X | Medications taken 1 month prior to enrollment, at the time of signing the informed consent and after signing the informed consent must be recorded on the appropriate CRF page |
| Safety Assessments | | | |
| Full Physical Examination | X | | Includes assessment of signs of thromboembolism or bleeding |
| Vital Signs | X | | Heart Rate, BP, respiratory rate and temperature |
| Assessment of Signs and Symptoms | | X | Signs and symptoms of thromboembolism or bleeding |
| Serious Adverse Events Assessment | X | X | Collection of SAEs begins after signed consent |
| Adverse Events Assessment | | X | Collection of non-serious AEs begins after randomization |

Table 5.1-1: Screening Procedural Outline (CV185362)

| Procedure | Consent/ Screening Visit Day -21 to 1 | Randomization Visit Day 1 | Notes |
|---|---|---------------------------------|--|
| Laboratory Tests | X | | 
CBC, ALT, AST, total and conjugated bilirubin, serum creatinine, aPTT, and INR.
 
To avoid unnecessary blood draws, safety labs including CBC, liver and renal function tests, coagulation tests that are run 1 to 7 days prior to the consent/screening visit as part of routine clinical care may be used to satisfy the inclusion/exclusion criteria as long as the investigator believes the lab values could not have changed at enrollment
 
Approximately 3-5 ml of blood
 |
| Pregnancy Test WOCBP only | X | | 
Negative serum or urine pregnancy tests (minimum sensitivity 25 IU/L or equivalent units of HCG) for WOCBP within 24 hours prior to start of study drug.
 
Note: an extension up to 72 hours is permissible in situations where pregnancy test results cannot be obtained within the standard 24 hour window
 |
| PK Sampling Apixaban subjects only | | X | 
Day 1: 4hr (3-8hr) post dose
 
Each sample will be approximately 1.4 mls of blood for children < 1 year of age and approximately 2 ml of blood for children ≥ 1 year of age and will be for both PK and anti-Xa activity assay
 
PK collection with dried blood spot (DBS) technique is an option for those children < 3 months at randomization. If DBS collection is chosen, a serum PK sample must also be obtained on Day 1
 
The Day 1 post dose 4 hr sample should be taken 3-8 hrs after the first apixaban dose. For those subjects on VKA prior to study entry who are randomized to apixaban, and have to wait for their INRs to be below 2 before starting apixaban, the Day 1 post dose 4 hr sample should be postponed and only be done 3-8 hr after the subject has taken their first dose of apixaban
 |
| Anti-Xa activity Apixaban subjects only | | X | 
Day 1: 4hr (3-8 hr) post dose
 
Each sample will be approximately 1.4 mls of blood for children < 1 year of age and approximately 2 ml of blood for children ≥ 1 year of age and will be for both PK and anti-Xa activity assay
 
For those subjects on warfarin who are randomized to apixaban and have to
 |

Table 5.1-1: Screening Procedural Outline (CV185362)

| Procedure | Consent/ Screening Visit Day -21 to 1 | Randomization Visit Day 1 | Notes |
|---|---|---------------------------------|---|
| | | | wait for their INRs to be within range before starting apixaban, the Day 1 post dose 4 hr sample should be postponed and only be done 3-8 hr after the subject has taken their first dose of apixaban For those children < 3 months of age at randomization, blood samples will not be taken at Day 1. |
| Chromogenic FX assay Apixaban subjects only | | X | Day 1 Prior to 1st dose, 4 hr (3- 8 hr) post dose Each sample will be approximately 1.4 ml of blood For those subjects on warfarin who are randomized to apixaban and have to wait for their INRs to be within range before starting apixaban, the Day 1 post dose 4 hr (3-8 hr) sample should be postponed and only be done 3-8 hr after the subject has taken their first dose of apixaban |
| | | | |
| Efficacy Assessments | | | |
| QOL assessment | | X | PedsQL and KIDCLOT QOL instruments to be administered to English speaking subjects who have been previously taking an anticoagulant. Subjects newly taking anticoagulants will be given the PedsQL only at this visit. The QOL instruments needs to be completed at the time of the visit |
| Study Drug Supplies | | | |
| Enroll via IWRS | X | | |
| Randomize via IWRS | | X | Subjects can be enrolled and randomized during the same visit. |
| Dispense Study Drug | | X | Apixaban, warfarin and enoxaparin will be supplied by BMS or warfarin and |

Table 5.1-1: Screening Procedural Outline (CV185362)

| Procedure | Consent/ Screening Visit Day -21 to 1 | Randomization Visit Day 1 | Notes |
|------------------------|--|--|--|
| | | | LMWH will be sourced locally by the study site. Study drug diaries will be used to record study drug administration. |
| Dispense Patient Diary | | X | Patient diary will be used to collect dose, date, and time of when study medication is administered to the subject |

Table 5.1-2: Study Procedural Outline (CV185362)

| Procedure | During Treatment ^d | | | | | End of Treatment | Follow-up | Notes |
|-----------------------------------|-------------------------------|---|-------------------|--------------------------------|-------------------|---|---|--|
| | Week 2 ± 3 days | Week 6 ± 3 days (only subjects < 3 months at time of randomization) | Month 3 ± 2 weeks | Month 6 ± 2 weeks ^e | Month 9 ± 2 weeks | Month 12 ± 2 weeks or early drug discontinuation | Month 14 ± 2 weeks (or 2 months after the end of anticoagulation) | |
| Concomitant Medication Assessment | X | | X | X | X | X | X | Subjects ≥ 2 years of age have the option of an in-person or a phone call visit at 9 months ± 2 weeks. Subjects < 2 years of age are required to have an office visit |
| Body Weight | | X | X | X | X | X | | Apixaban dose should be adjusted based on body weight changes according to dosing guidance document provided to the site. Subjects ≥ 2 years of age have the option of an in-person or a phone call visit at 9 months ± 2 weeks. Body weight will only be taken at the office visits |
| Safety Assessments | | | | | | | | |
| Targeted Physical Examination | X | | X | X | | X | | Includes organ systems pertinent to the subject's signs, symptoms, or adverse events, e.g., assessment of signs of bleeding |
| Vital Signs | X | | X | X | | X | | Heart Rate, BP, respiratory rate and temperature |
| Serious Adverse Event Assessment | X | X | X | X | X | X | X | Collection of SAEs begins after signed consent. Subjects ≥ 2 years of age have the option of an in-person or a phone call visit at 9 months ± 2 weeks. The 6 week visit is only for those subjects < 3 months. |
| Adverse Events Assessment | X | X | X | X | X | X | X | Collection of non-serious AEs begins after randomization. Subjects ≥ 2 years of age have the option of an in-person or a phone call visit at 9 months ± 2 weeks. The 6 week |

Table 5.1-2: Study Procedural Outline (CV185362)

| Procedure | During Treatment ^d | | | | | End of Treatment | Follow-up | Notes |
|---|-------------------------------|---|-------------------|--------------------------------|-------------------|---|---|--|
| | Week 2 ± 3 days | Week 6 ± 3 days (only subjects < 3 months at time of randomization) | Month 3 ± 2 weeks | Month 6 ± 2 weeks ^e | Month 9 ± 2 weeks | Month 12 ± 2 weeks or early drug discontinuation | Month 14 ± 2 weeks (or 2 months after the end of anticoagulation) | |
| | | | | | | | | visit is only for those subjects < 3 months. |
| Laboratory Tests ^a | X | | X | X | | X | | CBC, ALT, AST, total and conjugated bilirubin for all subjects. INR for subjects receiving VKA or anti-Xa activity for subjects receiving LMWH as per SOC |
| Pregnancy Test WOCBP only | X | | X | X | | X | | |
| | | | | | | | | |
| PK, PD [REDACTED] | | | | | | | | |
| PK Sampling Apixaban patients only ^b | X | | X | X | | | | Week 2: Pre-dose sample Month 3: 2 ± 1 hr post dose sample Month 6: Pre-dose sample For those children < 3 months of age at randomization, blood samples will only be taken at Day 1, Week 2, and Month 3. A dried blood spot technique can be used for PK sampling in children < 3 months of age at randomization |
| Anti-Xa Sampling Apixaban | X | | X | X | | | | Week 2: Pre-dose sample |

Table 5.1-2: Study Procedural Outline (CV185362)

| Procedure | During Treatment ^d | | | | | End of Treatment | Follow-up | Notes |
|--|-------------------------------|---|-------------------|--------------------------------|-------------------|---|---|--|
| | Week 2 ± 3 days | Week 6 ± 3 days (only subjects < 3 months at time of randomization) | Month 3 ± 2 weeks | Month 6 ± 2 weeks ^e | Month 9 ± 2 weeks | Month 12 ± 2 weeks or early drug discontinuation | Month 14 ± 2 weeks (or 2 months after the end of anticoagulation) | |
| patients only ^b | | | | | | | | Month 3: 2 ± 1 hr post dose sample Month 6: Pre-dose sample For those children < 3 months of age at randomization, blood samples will only be taken at Month 3. |
| Chromogenic FX Assay Sampling Apixaban patients only ^b | | | X | X | | | | Month 3: 2 ± 1 hr post dose sample Month 6: Pre-dose sample For those children < 3 months of age at randomization, blood samples will only be taken at Day 1 and Month 3. |
| | | | | | | | | |
| Efficacy Assessments | | | | | | | | |
| QOL assessment | X | | | X | | X | | If the subject is just starting an anticoagulant, KIDCLOT only to be completed by English speaking subjects at Week 2 visit. The QOL will be completed for all subjects at the Month 6 visit, and the end of study treatment (for subjects who discontinue study drug early) or Month 12 visit. The QOL needs to be completed at the time of the visit |
| Thromboembolic events | X | | X | X | X | X | X | Record thromboembolic events in the appropriate CRF page; send pertinent documents for adjudication. Subjects |

Table 5.1-2: Study Procedural Outline (CV185362)

| Procedure | During Treatment ^d | | | | | End of Treatment | Follow-up | Notes |
|--------------------------|-------------------------------|--|-------------------|--------------------------------|-------------------|--|---|---|
| | Week 2 ± 3 days | Week 6 ± 3 days (only subjects < 3 months at time of randomization) | Month 3 ± 2 weeks | Month 6 ± 2 weeks ^e | Month 9 ± 2 weeks | Month 12 ± 2 weeks or early drug discontinuation | Month 14 ± 2 weeks (or 2 months after the end of anticoagulation) | |
| | | | | | | | | ≥ 2 years of age have the option of an in-person or a phone call visit at 9 months ± 2 weeks |
| Study Drug | | | | | | | | |
| Dispense Study Drug | | X* | X | X | X* | | | *For subjects who will have a Week 6 or Month 9 office visit, study medication will be dispensed. Dose will be adjusted for weight gain if necessary. Study drug diaries will be used to record study drug administration |
| Collect Patient Diary | | | X | X | X | X | | If subject is there for an office visit, verify patient diary completion, study drug compliance, and dispense patient diary back to subject |
| End taking Study Drug | | | | | | X | | The study medication will start on Day 1 and continue up to 12 months or until the need for anticoagulant is resolved, whichever is shorter. |

^a INR levels for subjects receiving VKA and anti-Xa levels for subjects receiving LMWH as part of SOC will also be collected between visits per SOC and recorded at each visit. Those INRs collected between visits via a home monitoring device will be logged in diaries and recorded at the subsequent visit.

^b For subjects who discontinue before the month 6 visit, blood samples will be taken at the end of the treatment discontinuation + 2 weeks.

^d Week 6 visit only for those subjects < 3 months of age at the time of randomization

e No PK/FXa/chromogenic samples taken at Month 6 for children < 3 months

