Subjects eligible for the study include both males and females, 28 days to < 18 years of age, with congenital or acquired heart disease who are at risk for thrombus formation that can result in vascular, intracardiac or coronary artery thrombosis, or embolization to other organs or tissue, and who require chronic anticoagulation for thromboprophylaxis as determined by the treating physician with guidance from major current guidelines (ACCP 2012 guideline). To be eligible for the study, subjects under age 2 years should be expected to require anticoagulation for a minimum of 1 month; whereas subjects ≥ 2 years of age should be expected to require anticoagulation for a minimum of 6 months, although the full treatment duration of 12 months is most desirable. Subjects who are expected to be chronically anticoagulated (> 1 year), should have a study treatment duration of 12 months. Eligible subjects include those who newly start anticoagulants and those who are currently on VKA or LMWH for thromboprophylaxis. The investigator is responsible for working with the treatment team to determine if a subject meets the criteria for thromboprophylaxis per the current ACCP guideline. The reasons the subject is receiving prophylaxis will be documented on the eCRF.

Three age groups will be included in the study: 28 days to < 2 years, 2 years to < 12 years, and 12 years to < 18 years. Every effort will be made to ensure appropriate representation for each of the age groups. The neonate cohort will be removed from the study population [redacted] upon approval of this revised protocol.

[redacted] Recruitment started in January 2017 for children of ages ≥ 2 to < 18 years and was extended to children ages 3 months to < 2 years in December 2017. Recruitment opened to children 28 days to < 3 months old in February 2020.

Key Inclusion Criteria:

1. Males and females, 28 days to < 18 years of age
2. Congenital or acquired heart diseases requiring chronic anticoagulation for thromboprophylaxis (e.g., single ventricle physiology including all 3 stages of palliation, dilated cardiomyopathy, Kawasaki disease with coronary aneurysms, and pulmonary hypertension).
Note: subjects with previous history of thromboembolic events greater than 6 months prior to enrollment are eligible, provided there is evidence (by previously obtained clinical imaging data) for thrombus stability or resolution.

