1.3.2 Secondary Objectives

In pediatric subjects with congenital or acquired heart disease requiring chronic anticoagulation for thromboprophylaxis:

- To assess apixaban PD by measuring FX using chromogenic assay and anti FXa activity
- To compare the effects of apixaban on QOL measures versus VKAs antagonists or subcutaneous LMWH
- To gather exploratory data on the efficacy of apixaban

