Consistent with its mechanism of action, apixaban can increase clotting time measures such as activated partial thromboplastin time (aPTT), International Normalized Ratio (INR) as well as affect other coagulation assessments (anti-Xa activity, thrombin generation, etc.). However, apixaban has been shown to have minimal impact on the aPTT, or INR at therapeutic concentrations. Measurement of anti-FXa activity, using a one-step chromogenic assay is appropriately sensitive enough to detect its presence²⁶.

To support the apixaban pediatric development plan, additional clinical pharmacology studies have been completed and are described below.

The palatability and relative bioavailability of apixaban oral solution have been assessed in healthy adult subjects. Based on these studies the apixaban oral solution is expected to have acceptable palatability for the pediatric population and has comparable bioavailability to the apixaban tablet formulation. In addition, administration of the oral solution or a crushed tablet via a NGT flushed with 60 mL D5W achieves similar exposure to oral administration of the apixaban solution. Apixaban relative bioavailability appears to be 8% to 20% lower following administration of the oral solution via NGT using infant formula or an enteral meal, such as Boost Plus, as a flush medium.

The palatability and relative bioavailability of apixaban 0.1 mg capsules dispersed in water relative to the 0.5 mg tablets dispersed in water have been assessed in healthy adult subjects. Based on this study, both of these pediatric formulations are expected to have acceptable palatability. The results of this study demonstrated comparable AUC was achieved with both formulations, but the C_{max} was ~30% higher with the 0.1 mg capsule formulation compared to the 0.5 mg tablet formulation.

[figure not shown]
An in vitro comparison study was performed in pediatric and adult plasma samples spiked with apixaban to compare and characterize the PD activity of apixaban in pediatric and adult plasma samples. This study demonstrated that, relative to adults, Factor X levels are lower in plasma samples from children 6 months of age and younger as well as in umbilical cord blood; this observation is consistent with literature reports of developmental hemostasis. Despite the lower

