Table 5.5-3: Sampling Schedule for PK and PD using serum samples for children 28 days to < 3 months of age

| Procedure | Subjects | Day 1 ^{a, b} | Week 2 ^b ± 3 days | Month 3 ^b ± 2 weeks | Whole Blood Volume |
|-------------------|--------------------------|----------------------------------|---------------------------------|-----------------------------------|--|
| Serial PK | Subjects taking Apixaban | 4 hr (3-8 hr) | Pre-dose | 2 ± 1 hr Post dose | 1.4 ml sample for PK and anti-FXa combined |
| Anti-FXa activity | Subjects taking Apixaban | | | 2 ± 1 hr Post dose | |
| Chromogenic FX | Subjects taking Apixaban | Prior to first dose ^c | | 2 ± 1 hr Post dose | 1.4 mL / sample |

a The Day 1 post dose 4 hr (3-8 hr) sample should be taken 3-8 hrs after the first apixaban dose. For those subjects on VKA prior to study entry who are randomized to apixaban, and have to wait for their INRs to be below 2 before starting apixaban, the Day 1 post dose 4 hr (3-8 hr) sample should be postponed and only be done 3-8 hr after the subject has taken their first dose of apixaban.

b For subjects undergoing surgery and possibly getting a transfusion, the PK/PD and chromogenic FX [REDACTED] samples should be drawn before the transfusion or surgery or at least a week after surgery

c Blood samples can be taken any time prior to the first dose of study drug at randomization (Day1).

Table 5.5-4: Sampling Schedule for PK and PD using dried blood spot (DBS) sampling for children 28 days to < 3 months of age^d

| Procedure | Subjects | Day 1 ^{a, b, c, d} | Week 2 ^b ± 3 days | Month 3 ^b ± 2 weeks | Whole Blood Volume |
|------------------------|--------------------------|----------------------------------|---------------------------------|-----------------------------------|---|
| Serial PK ^c | Subjects taking Apixaban | 4 hr (3-8 hr) | Predose | 2 ± 1 hr Post dose | 1.4 ml serum sample for PK at Day 1 only |
| Anti-FXa activity | Subjects taking Apixaban | | | 2 ± 1 hr Post dose | PK and anti-FXa sample combined |
| Chromogenic FX | Subjects taking Apixaban | Prior to first dose ^c | | 2 ± 1 hr Post dose | 60-80 uL for PK DBS samples at Day 1, Week 2, and Month 3 |
| | | | | | 1.4 mL / sample |

[figure not shown]

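### Infants 28 days to <3 months at randomisation have no routine on-drug PD sample before about 3.4 months of age, and the early-discontinuation sample that could fill the gap is inconsistently defined

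*Combined protocol and SAP*

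**What the plan says.** Section 1.3.2 sets a secondary objective for the whole paediatric population: "To assess apixaban PD by measuring FX using chromogenic assay and anti FXa activity". For the youngest infants the schedule is as follows.

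- **Anti-FXa.** Table 5.1-1 says "For those children < 3 months of age at randomization, blood samples will not be taken at Day 1". Table 5.1-2 says "For those children < 3 months of age at randomization, blood samples will only be taken at Month 3". Synopsis Tables 1.3 and 1.4, Tables 5.5-3 and 5.5-4, and Appendix 1 Tables 2 and 3 agree.
- **Chromogenic FX.** Table 5.1-2 says "For those children < 3 months of age at randomization, blood samples will only be taken at Day 1 and Month 3". Tables 1.3, 1.4, 5.5-3 and 5.5-4 and Appendix 1 Tables 2 and 3 make the Day 1 draw pre-dose only. Table 5.1-1 lists "Day 1 Prior to 1st dose, 4 hr (3- 8 hr) post dose" and gives no exemption for this band.
- **Month 6.** No PK or PD sample.
- **PK.** Day 1 (3-8 h post dose), Week 2 (pre-dose) and Month 3. Table 5.5-3 gives the volume as "1.4 ml sample for PK and anti-FXa combined".
- **Course length.** Eligibility requires only that "subjects under age 2 years should be expected to require anticoagulation for a minimum of 1 month".
- **Early discontinuation.** Footnote b of Table 5.1-2, attached to the PK, anti-Xa and chromogenic FX rows, calls for samples at discontinuation plus two weeks. Footnote c of Appendix 1 Tables 2 and 3, attached to the same three assays, calls for them at discontinuation and mentions no two weeks. Tables 1.3, 1.4, 5.5-3 and 5.5-4 contain no such sample.

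Section 1.4 reports that, "relative to adults, Factor X levels are lower in plasma samples from children 6 months of age and younger".

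**The concern.** Section 1.4 describes this age range as different in two ways: endogenous FX is low, and apixaban clearance shows a trend with age below 3 months. It is also where the smallest weight tiers apply. Yet the plan measures drug effect here once per child, after the child has left the age band. A child on a short course may have stopped by then.

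Children of 3 months and older have FX drawn before and 3-8 h after the first dose on the same day, a contrast that growth cannot disturb. The youngest infants lose that contrast and are left with two values 76 to 104 days apart. FX is drawn only in apixaban subjects, so no comparator series shows how FX moves with age.

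At stake is how far section 8.1's aim of characterising PK and PD from 28 days of age rests on measurement, and how far on extrapolation from older infants.

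**Working it through.** **1. The scheduled draws, checked against the plan's own volumes (Appendix 1 Table 2).** Safety laboratory tests take 3-5 mL; each PK or FX tube takes 1.4 mL.

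- Low end: 3 + (1.4 + 1.4) + (3 + 1.4) + (3 + 1.4 + 1.4) + 3 + 3 = 22.0 mL.
- High end: 5 + 2.8 + 6.4 + 7.8 + 5 + 5 = 32.0 mL.

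Both match the stated 22-32 mL. The Day 1 figure of 2.8 mL is one PK tube plus one pre-dose FX tube. A post-dose FX tube would make Day 1 4.2 mL and the total 23.4-33.4 mL. The Day 1 post-dose FX entry in Table 5.1-1 therefore appears not to be meant for this band, but the text does not say so. The dried-blood-spot table gives 2.88 mL on Day 1 (2.8 mL plus 0.08 mL), with the same implication. Its column totals add to 20.04-30.04 mL against a stated 20.4-30.4 mL, a side point.

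**2. Age at the only routine on-drug PD sample.** A month is 30 days, so Month 3 ± 2 weeks = 90 ± 14 = Day 76 to 104. Age at randomisation runs from 28 to just under 90 days.

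- Youngest: 28 + 76 = 104 days; 104 / 30.4375 = 3.4 months.
- Oldest: 90 + 104 = 194 days; 194 / 30.4375 = 6.4 months (taking 3 months as 91 days gives 195 days, also 6.4).
- At nominal Day 90: 118 to 180 days, or 3.9 to 5.9 months.

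No value falls below 3 months of age.

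**3. Short courses.** A child who stops before Day 76 is off drug throughout the Month 3 window. A child who stops between Day 76 and Day 104 may or may not be, depending on the visit date.

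**4. What the discontinuation sample would give after a 30-day course.** Assume age at randomisation is uniform over the 62 days from 28 to 90.

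| Timing | Age at sample | Share under 90 days old |
|---|---|---|
| At the last dose | 58 to just under 120 days | (90 − 30 − 28) / 62 = 52% |
| 14 days later | 72 to just under 134 days | (90 − 44 − 28) / 62 = 29% |

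Section 4.5.2 gives an effective half-life of about 12 h. Fourteen days is 14 × 24 / 12 = 28 half-lives, leaving 2^-28, or 4 parts in 10^9. That half-life may not hold in young infants, so as a range: at 24 h, 2^-14 = 0.006% remains; at 48 h, 2^-7 = 0.8%. In each case the sample is in effect drug-free.

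The two weeks could instead be a visit window. Even then, at 12 h, one day off drug leaves 2^-2 = 25% and three days leave 2^-6 = 1.6%. Without a recorded time since last dose the value could not be placed.

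**5. What the tubes already drawn could give.** Day 1 precedes 3 months of age in every infant who starts drug promptly after randomisation. At nominal Week 2, on the same uniform assumption, (90 − 14 − 28) / 62 = 77% are still under 90 days old. In the 3-month to <1-year band, Table 5.5-2 has the same 1.4 mL serve both PK and anti-FXa at Day 1 and Week 2.

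**The case against.** The strongest reply is that the gap is limited and partly deliberate.

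- **The objective is not set by age band.** Section 1.3.2 covers all paediatric subjects, and the randomisation stratum is 28 days to <2 years. A reader might infer that PD cannot be assessed in this band. The documents do not support that. Infants still treated at Month 3 give on-drug PD and at nominal timing are under 6 months old, the range section 1.4 gives for low FX. Section 8.1 pools the data with two other paediatric studies, and the single-dose study includes 9 subjects aged 28 days to <9 months.
- **A discontinuation sample exists.** A reader of Tables 5.5-3 and 5.5-4 alone might infer that a 30-day course yields no on-drug PD value. Footnote b of Table 5.1-2 and footnote c of Appendix 1 Tables 2 and 3 both order one, so zero is not established. What can be said is that its timing is contradictory.
- **PK covers part of the anti-FXa gap.** Section 5.5 uses anti-FXa to assess apixaban levels. Concentration is measured directly at three visits, and section 1.4 reports a linear relation between the two. This stands for anti-FXa. It does not cover FX inhibition, where section 1.4 reports 17% and 16% greater inhibition in infant and neonate plasma than in adult plasma, although it calls the effect generally consistent with adults.
- **No change-from-baseline FX analysis is prescribed.** Section 8.4.4 defers methods to a separate PK/PD plan. Bias from maturing FX is therefore a risk to guard against, not an error in a stated analysis, and the documents give no rate of FX rise.
- **Blood is scarce in these infants.** True, but running an assay on a tube already drawn takes none.

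**Conclusion.** The point holds in a limited form. In this band the only routine on-drug anti-FXa and chromogenic FX sample is at Month 3, at about 3.4 to 6.4 months of age, so routine on-drug PD below 3 months is nil. A child who stops before Day 76 depends on a discontinuation sample that the tables define in two ways or omit. Read literally with the two weeks added, that sample is drug-free.

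The age result rests only on the protocol's 30-day month and visit window. The 52%, 29% and 77% shares rest on the uniform-age assumption. The drug-free conclusion holds across half-lives of 12 to 48 h. The documents do not say how many infants will be in this band or will stop before Day 76, so the number affected is unknown. This is an inexpensive improvement and a needed reconciliation. It does not undermine the trial's safety objective or its population-wide PD objective.

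**What to change.** 1. **Anti-FXa on existing tubes.** In Tables 1.3, 1.4, 5.1-1, 5.1-2, 5.5-3 and 5.5-4 and Appendix 1 Tables 2 and 3, add anti-FXa on the 1.4 mL PK tube at Day 1 (3-8 h) and, where venous sampling is used, at Week 2. For dried-blood-spot infants use the Day 1 tube, which is drawn anyway. The laboratory manual should first confirm that the tube suits the assay, because some tables call it serum while section 8.4.4 says plasma. Anti-FXa values per infant treated through Month 3 rise from one to three (venous) or two (dried blood spot). The cost is the assays and less residual sample, with no extra blood.
2. **One discontinuation rule.** Reconcile the footnotes across all these tables so that, in infants stopping before Month 3, the PK, anti-FXa and FX sample is collected while the child is still on drug, with time since last dose recorded. The Week 6 visit (Day 39 to 45) cannot be the general answer, because a 30-day course ends before it. This retimes a sample that the footnotes already order.
3. **Day 1 FX.** Reconcile the post-dose entry in Table 5.1-1 with Table 5.5-3 and the 2.8 mL Day 1 volume.
4. **FX analysis (secondary).** Have the PK/PD plan relate FX to concurrent apixaban concentration and age at sampling. In this band it should not read Month 3 minus baseline change as inhibition. This needs only analysis text.

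Items 1 to 3 need a sampling-table amendment and a laboratory-manual update.
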